**PATCH – Pelvis Protocol v5**  
**12/20/16**

*Potential Confounding Variables*

The following variables will be abstracted from the medical record by research staff:

- (1) Age
- (2) Gender
- (3) Body mass index
- (4) Comorbidities (history of diabetes or cardiac disease)
- (5) Anticoagulant use

The following variables will be determined by an orthopaedic surgeon based on data abstracted from the medical record:

- (6) Injury severity score
- (7) Fracture severity: defined by the Young and Burgess and AO/OTA classification of pelvic fractures

Methodology

*Application of inclusion and exclusion criteria:* Awake patients will be asked at the scene for their age (inclusion criteria 1), mechanism of injury (inclusion criteria 2), and presence of pelvic, hip, or groin pain (inclusion criteria 3). Patients who state they sustained a ground level fall will be excluded (exclusion criteria 1). The age of obtunded patients will be determined using personal identification (e.g. driver's license) if available but will otherwise be estimated by EMS personnel. EMS personnel will evaluate patients for signs of pelvic injury (inclusion criteria 4) and hemodynamic instability (inclusion criteria 5). Based on the location of the scene and severity of the injuries, EMS personnel and their dispatcher will determine whether participating hospital or a different facility will receive the patient (exclusion criteria 2).

*Randomization:* Prior to each shift, each ambulance will be randomly assigned an opaque box containing either a commercial pelvic binder or a weight-equivalent object and patient ID tag. When an ambulance arrives at the scene, EMS personnel will apply inclusion and exclusion criteria to determine if the patient is appropriate for this study. If so, EMS personnel will open the opaque box. If the box contains a pelvic binder, the patient will have a pelvic binder placed. If the opaque box contains the weight-equivalent object, the patient ID tag will be clipped to the patient, and the patient will be managed without a binder under the current standard of care. At the receiving facility, EMS personnel will page the research team and fill out the label on the box with information identifying the run number, unit number, and time of dispatch. The box will be placed in a box in the emergency department for research staff to pick up. The removal of pelvic binder on patient will be determined by the appropriate physician team. Pelvic binder should be removed within 72 hours of admission.

*Collection of prehospital outcome data:* At the time of initial assessment by EMS personnel, awake patients will be asked to rate their pain using a visual analog scale (VAS). At the conclusion of ambulance transport, awake patients will again be asked to rate their pain using a VAS. The patient's initial heart rate and blood pressure will also be recorded in the prehospital environment.

*Collection of data in the hospital environment:* Patients enrolled in the study will be identified using the information collected by EMS personnel on the box, the page to research staff, and/or the presence of a pelvic binder or patient ID tag on the patient. Primary outcome data will be abstracted from the medical record. The patient's initial heart rate and blood pressure will be recorded upon presentation to the Emergency Department (ED). Other laboratory data, including lactate, base deficit, hemoglobin, and PT/INR, will be collected upon presentation to the ED. Pelvic radiographs will be obtained as appropriate per standard of care. Both placement and location of the pelvic binder upon arrival will be determined from pelvic radiographs. Whether or

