**PATCH – Pelvis Protocol v5**  
**12/20/16**

- (2) Traumatic injury other than ground-level fall (e.g. MVC, MCC, fall from height  $\geq 20$  feet, etc.), *and*
- (3) Complaint of pelvic, groin, or hip pain, *or*
- (4) Pelvic or hip deformity, ecchymosis, or crepitus in an obtunded patient, *or*
- (5) Hemodynamic instability:
  - a. Systolic blood pressure  $\leq 90$  mmHg
  - b. Heart rate  $>100$  BPM

*Exclusion Criteria:*

- (1) Ground level fall.
- (2) Penetrating pelvis injury without frank evidence of fracture.
- (3) Obviously pregnant patients
- (4) Patients who are too small ( $<32$ in) or too big ( $>50$ in) for the binder
- (5) Priority 2 or 3 Trauma

*Representativeness of the Sample:* Our study should capture a large portion of the patients who present to the hospital with pelvic trauma. We chose to exclude patients who sustained a ground level fall. These are low-energy mechanisms of injury less likely to be improved by external pelvic compression, and more likely to have skin compromise.

Definition of Variables:

*Primary Outcome Variables:* These variables will be abstracted from the medical record by research staff.

- (1) Initial heart rate and blood pressure at the scene (pre-hospital)
- (2) Initial heart rate and blood pressure upon arrival at the Emergency Department
- (3) Time of injury, EMS arrival, binder application (if done), ED arrival
- (4) Initial labs upon arrival at the Emergency Department: lactate, base deficit, PT/INR, hemoglobin
- (5) 24-hour transfusion requirements
- (6) 48-hour transfusion requirements
- (7) Need for angioembolization
- (8) Need for surgical control of bleeding
- (9) Length of intensive care unit stay
- (10) Length of hospital stay
- (11) Need for readmission
- (12) 30-day mortality
- (13) Location of pelvic binder upon presentation to the hospital
- (14) Time the binder removed
- (15) Skin compromise attributable to binder use (location and time since binder placement)
- (16) Other complications of binder use (description and time since binder placement)

*Secondary Outcome Variables:* These variables will be reported by non-obtunded patients using a Visual Analog Score in the pre-hospital environment.

- (1) Pain score at presentation
- (2) Pain score at the conclusion of ambulance transfer (upon arrival to the Emergency Department)

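### Allocation is revealed at the scene with no record at opening or box count described, one of three routes for finding enrolled patients differs by arm, and the destination exclusion is not in the listed criteria

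*Combined protocol and SAP*

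**What the plan says.** All references are to the combined protocol and SAP.

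- **Randomization.** Before each shift every ambulance receives "an opaque box containing either a commercial pelvic binder or a weight-equivalent object and patient ID tag". At the scene the crew applies the criteria to "determine if the patient is appropriate for this study. If so, EMS personnel will open the opaque box". A binder box leads to a binder being placed. For the other box, "If the opaque box contains the weight-equivalent object, the patient ID tag will be clipped to the patient". The study records come after transport: "At the receiving facility, EMS personnel will page the research team and fill out the label on the box". The label holds run number, unit number and dispatch time, and the used box is left in the emergency department (ED) for collection.
- **Collection of data in the hospital environment.** Enrolled patients are found from the box information, the page, or a binder or tag seen on the patient, joined by and/or. Binder placement and position are read from pelvic radiographs, which are taken where standard care calls for them. Removal of the binder in the ED is left to the treating physician on clinical grounds.
- **Primary Outcome Variables.** Of the 16 listed items the plan says: "These variables will be abstracted from the medical record by research staff".
- **Data analysis.** An intention-to-treat analysis is promised, without saying which patients form that population.
- **Application of inclusion and exclusion criteria.** "Based on the location of the scene and severity of the injuries", the text continues, "EMS personnel and their dispatcher will determine whether participating hospital or a different facility will receive the patient (exclusion criteria 2".
- **Exclusion Criteria.** The item with that number reads "2) Penetrating pelvis injury without frank evidence of fracture".

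**The concern.** A patient counts as randomized once the box is opened. As described, nothing is written down at that moment, and nothing later establishes how many boxes were opened. If a patient is then not identified in hospital, the record is never abstracted, the intention-to-treat analysis cannot include that patient, and no one would know.

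The routes for finding patients are also not fully the same in the two arms. If the shared routes fail, whether a patient is found depends on noticing a binder in one arm and a tag in the other. Ascertainment that depends on allocation can undo the balance that randomization provides. The planned comparison of baseline variables would not reveal it, because it can use only patients who were found.

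The destination rule bears on the same issue. It decides who reaches the place where the page and label are completed, yet it does not appear in the list of exclusions that crews are to apply.

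**Working it through.** The plan gives no figure to reproduce, so the check is textual.

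**1. Order of events (Randomization).** Box issued to ambulance; criteria applied at the scene; box opened and allocation seen; binder placed or tag clipped; transport; page and label at the receiving facility; box left for collection. The binder and tag are physical markers from the scene onward, but they are not records. No log of issued boxes, entry at opening or count of returned boxes is described. The run number could later allow a link to dispatch records, but no such check is described, and the number goes on the label only after arrival.

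**2. Identification routes, by arm.**

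| Route | Binder arm | Control arm | Where completed |
|---|---|---|---|
| Box label | same | same | receiving facility |
| Page | same | same | receiving facility |
| Marker on patient | binder | clipped tag | applied at scene |

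Two of three routes are completed at the receiving facility, and one of three differs by arm. The wording on box contents could mean that both box types hold a tag, but clipping is described only for controls.

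**3. What a loss requires.** Any one route is enough to find a patient. A missed patient therefore needs the page not sent, the label or box not usable, and the marker not noticed. Only the last of these differs by arm.

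**4. Direction.** A binder may be taken off in the ED, partly according to hemodynamic stability and imaging, which would weaken that marker. On the other hand, it may show on a pelvic radiograph, and its application time, location and removal time are among the items to be abstracted, so it may leave traces in the record after removal. Nothing is said about removal of the tag, or about any trace of it in the chart. The asymmetry could run either way.

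**5. What is lost with a missed patient.** All 16 listed primary items. Four of them (items 13 to 16) concern the binder only, so 16 − 4 = 12 have a control-arm counterpart, one of those (the list of times) in part.

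**6. Cross-references.** The application text cites seven numbered criteria: inclusion 1 to 5 and exclusion 1 and 2. Six agree with the lists. The seventh, exclusion 2, is used for destination but is listed as penetrating pelvis injury. Of the five listed exclusions, none concerns destination.

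**The case against.** The strongest reply is redundancy. There are three routes, any one suffices, the page and label do not depend on arm, and the opened box left in the ED is a further trace even with a blank label. Destination is handled among the eligibility checks, which come before opening, so the numbering fault could be editorial. Intention to treat conventionally means everyone randomized, and Data analysis already speaks of patients randomized to each group.

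Most of this stands, and it makes large losses less likely. It does not supply a denominator. No step is described that uses the returned box to count enrolments, and the page and label both rely on a crew that has already seen the allocation.

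A reader might infer three stronger things that the documents do not support:

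- *That patients whose binder is removed in the ED are lost from the binder arm.* They may still be found by page, label, radiograph or chart.
- *That a binder cannot identify a study patient, because the Background calls binders and sheeting the most common prehospital techniques.* That is a general statement, not one about this ambulance service. Controls are described as managed with no binder under current standard care, which points the other way.
- *That patients bound for other hospitals are being randomized and lost.* Read together, the eligibility and Randomization text places the destination decision before opening. A change of destination, or a death, after opening is simply not addressed.

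**Conclusion.** The point stands as a gap in tracking that should be closed. It is not a demonstrated bias. As described, randomized patients could be missed without being counted, and one identification route differs by arm. Without a count the team could not show that losses were few or balanced.

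The size cannot be derived: the documents give no share of patients taken elsewhere, no rate of missed pages or labels, and no recognition rate for either marker. The direction is unknown for the reasons in step 4.

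The mismatch on destination is certain from the text, and the two sections must be reconciled. Taken alone, that mismatch and the undefined intention-to-treat set would be matters of clarification; the arm-dependent marker and the missing count are what make a change worthwhile.

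This rests on two assumptions: that no box log or opening record exists outside the supplied text, from which some pages were removed, and that tags are clipped only to controls, as written.

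**What to change.** 1. Put the same serial-numbered ID tag in both box types and clip it to the patient in both arms.
2. At opening, have the crew record box number, run number and time, in the EMS run record or by a call to dispatch. Research staff hold the list linking serial number to arm and reconcile boxes issued, opened and returned, by arm. The entry has to be made at opening: if it relied on the label completed at the receiving facility, an unreturned box could not be classified as opened on a patient or lost unopened. Box numbers should not reveal the arm before opening.
3. Define the intention-to-treat set as every patient for whom a box was opened, including those diverted or dead before arrival, and report the number without outcome data by arm.
4. Make the Exclusion Criteria list and the cross-reference in the application text agree on destination.

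The cost is protocol wording, one tag per binder box, one extra crew entry per enrolment and a small reconciliation task for existing research staff. Patients diverted after opening may still lack outcomes, but they would be counted by arm. The log must be kept prospectively, because openings not recorded at the time may be impossible to reconstruct.

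### The crew judges a patient eligible before opening the box, but nothing records who that patient is, and no rule covers several eligible casualties, so a switch after the arm is seen could be neither prevented nor detected

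*Combined protocol and SAP*

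**What the plan says.** The Randomization paragraph under Methodology makes the ambulance and shift the unit of assignment: "Prior to each shift, each ambulance will be randomly assigned an opaque box". At the scene the order of steps is explicit. First, "EMS personnel will apply inclusion and exclusion criteria to determine if the patient is appropriate for this study". Next, "If so, EMS personnel will open the opaque box". Then the contents are acted on: "If the box contains a pelvic binder, the patient will have a pelvic binder placed"; with the weight-matched object instead, "the patient ID tag will be clipped to the patient, and the patient will be managed without a binder".

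Paperwork follows transport: "At the receiving facility, EMS personnel will page the research team and fill out the label on the box". The listed contents of the label are "information identifying the run number, unit number, and time of dispatch". They include neither a patient identifier nor a time of opening.

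The paragraph on data collection in the hospital finds enrolled patients through the box information, the page to research staff, the binder or tag on the patient, or a combination of these.

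The second inclusion criterion covers "Traumatic injury other than ground-level fall (e.g. MVC, MCC, fall from height" and similar mechanisms, and a complaint of pelvic, groin or hip pain is one qualifying route. Priority 2 and 3 trauma is excluded. No section mentions a scene with more than one eligible casualty. Data analysis plans baseline comparisons that include injury severity score and pelvic fracture class, and adds an intention-to-treat analysis.

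**The concern.** Motor vehicle collisions are an included mechanism, so two eligible casualties at one scene are foreseeable. Where a crew finds both eligible, the text does not say whose allocation the box holds. Once the box is open the crew knows the arm. If it holds the only binder to hand, there is an obvious pull towards the casualty who looks worse.

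If that happened in some binder boxes and not in control boxes, the arms would differ in severity before any treatment effect. Binders going to sicker patients would mask a benefit; the opposite habit would exaggerate one. Intention to treat keeps a randomized patient in the assigned arm, but it needs to know who that patient was independently of the arm. Here, every marker of enrolment is created after the arm is known.

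**Working it through.** **Order of steps, from the Randomization and hospital data paragraphs**

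| Step | Arm known? | Patient recorded? |
|---|---|---|
| Box assigned to ambulance before the shift | No | No patient yet |
| Criteria applied to the patient | No | No record required |
| Box opened | Yes, from here | No record required |
| Binder or tag put on | Yes | Only by wearing it |
| Page sent and label completed at the hospital | Yes | Run, unit and dispatch time only |
| Research staff identify enrolled patients | Yes | From the markers above |

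The eligibility decision is concealed. The identity of the patient it concerned is not captured until after concealment ends. Where one run involves two eligible casualties, the listed label items do not distinguish them.

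**Size.** The documents give no sample size, event rate or frequency of multi-casualty scenes, so there is no figure to reproduce. What follows is illustration on assumed inputs only.

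*Severity.* Let f be the share of opened boxes at scenes with two eligible casualties, and q the share of those where the crew selects after opening. With standard normal severity, the sicker of two lies on average 1/√π = 0.564 SD above the pair mean.

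- Selection in binder boxes only: shift = f × q × 0.564.
- Selection in both arms (the less injured gets the control tag): twice that.

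| f | q | Binder boxes only (SD) | Both arms (SD) |
|---|---|---|---|
| 2% | 25% | 0.003 | 0.006 |
| 5% | 100% | 0.028 | 0.056 |
| 10% | 50% | 0.028 | 0.056 |
| 20% | 100% | 0.113 | 0.226 |

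*Would the planned baseline tests show it?* Assume 200 per arm. The standard error of a difference in SD units is √(2/200) = 0.1. The chance of two-sided p < 0.05 is Φ(z − 1.96) + Φ(−z − 1.96), with z = shift/0.1:

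- 0.028 SD: z = 0.28, chance 0.06
- 0.113 SD: z = 1.13, chance 0.20
- 0.226 SD: z = 2.26, chance 0.62

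With no selection the chance is 0.05.

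*Mortality.* Spurious difference = f × q × (risk of the sicker casualty − pair mean), with selection in binder boxes only and no treatment effect.

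- Risks 15% and 5%: the bracket is 15 − 10 = 5 points. With f = 5% to 20%, q = 100% gives 0.25 to 1.0 point; q = 25% gives about 0.06 to 0.25.
- Risks 25% and 5%: the bracket is 25 − 15 = 10 points. With the same f, q = 100% gives 0.5 to 2.0 points; q = 25% gives about 0.13 to 0.5.

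The q = 100% figures suppose that every binder crew at such a scene departs from the written order. For each f they are upper values.

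**The case against.** A reader might infer that the protocol leaves the choice of patient open until the crew has seen the arm. It does not. Eligibility of the patient is settled first, the opaque box is opened only if that patient qualifies, and the sentence on placing the binder refers back to the same person. Moving the binder to another casualty after opening would depart from the procedure. Nor is assignment by ambulance a defect in itself: the box is opaque and weight-matched, so the arm is meant to stay concealed until eligibility is decided. All of this stands.

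Two further inferences also go too far. That a second eligible patient in a shift has no concealed allocation left is not established, because the text does not say whether a used box is replaced. In any case, a patient who is not enrolled is lost recruitment rather than bias between arms. Two ambulances attending one patient is not described either; it is a contingency worth a rule, not an error found in the plan.

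It is also fair that the Priority 2 and 3 exclusion makes paired eligible casualties less common, and that the baseline comparison of injury severity bears on the harm feared. But at the assumed 200 per arm that comparison would miss a 0.113 SD shift about 80% of the time (1 − 0.20), and finding an imbalance would not reveal who should have been enrolled.

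What survives is narrower: a correct order of steps that nothing on record can verify, and silence on the case where that order is ambiguous.

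**Conclusion.** The point holds as a gap in traceability. The protocol picks the patient before the arm is known, but requires no record of that choice until afterwards and gives no rule for several eligible casualties. Selection or switching after opening could therefore be neither prevented nor detected from the records it specifies, and the intention-to-treat analysis could not correct it.

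The documents do not show that switching occurred or would be common, and they fix neither the direction nor the size of any bias. The illustrative range is wide (0.003 to 0.226 SD in severity, about 0.06 to 2.0 points in mortality) and depends wholly on assumed frequencies, risks and crew behavior. The case for acting rests on the low cost of the remedy, and on the fact that the missing record cannot be reconstructed once patients have been enrolled without it.

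**What to change.** Amend the Randomization paragraph as follows.

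1. Before opening the box, the crew writes on the existing label a patient identifier, or a short descriptor where an obtunded patient has no identification, and the time.
2. The box belongs to the first patient that crew finds eligible. That patient counts as enrolled at opening and is analyzed in the box's arm, whatever device is worn afterwards.
3. If several ambulances attend one patient, the first box opened for that patient counts. Tying the arm to the transporting unit would be worse, since transport may be settled after opening and the arm would then depend on a later event.
4. Later eligible patients for whom no new sealed box has been issued are logged as not randomized.
5. Research staff reconcile every opened box to exactly one patient in the intention-to-treat set and report any that cannot be matched.

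These rules govern allocation, recording and analysis, and do not direct clinical care. The cost is one extra label line, a few seconds of writing at the scene before the box is opened, and brief crew training.

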**PATCH – Pelvis Protocol v5**  
**12/20/16**

not the pelvic binder is removed in the ED is based on clinical data (clinical evidence of hemodynamic stability, imaging failing to demonstrate a pelvic fracture) and is at the discretion of the treating physician (generally an emergency medicine physician or trauma surgeon) in the ED. Patients with evidence of hemodynamic instability or concern for ongoing hemorrhage will undergo angioembolization or surgical intervention according to our institution's protocol. Twenty-four and 48-hour transfusion requirements (including packed red blood cells, fresh frozen plasma, platelets, and cryoprecipitate); need for endovascular or surgical intervention for control of hemorrhage; and length of intensive care unit and hospital stay will be determined from the medical record. Thirty days after the injury, the need for readmission and all-cause mortality within this period will be recorded. Demographic and medical variables (BMI, history of cardiac disease, anticoagulant use, initial PT/INR) will also be abstracted from the medical record.

Complications of binder use, including skin compromise, will also be identified, as will the length of time between binder placement and each event. Should such an event occur a formal incident report will be filed with the appropriate hospital agency as well.

The fracture classification will be assigned by a fellowship-trained orthopaedic traumatologist. The type and timing of operative fixation of the patient's pelvic injury, if necessary, will be at the discretion of the treating orthopaedic surgeon.

*Data analysis:* Data analysis will be carried out when all patients have been assigned to either the experimental or control group. In order to determine whether the randomization process produced comparable groups, we will use t-tests and cross-tabulations to compare patients randomized to the pelvic binder group with those randomized to the control group. The following variables will be considered: age, gender, BMI, history of cardiac disease, anticoagulant use, PT/INR at presentation, injury severity score, and Young and Burgess pelvic fracture class. An intention to treat analysis will also be performed.

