The goal of external pelvic compression is stabilization of early clot. Historically, this has been attributed to reduction in pelvic volume; however, some studies suggest that splintage may actually be the mechanism (Ghaemmaghami 2007, Grimm 1989). Cadaveric and biomechanical studies suggest that these devices reduce both pelvic volume and motion in multiple planes (Bottlang JBJS 2002, Bottlang JOT 2002, Prasarn 2013). What is not known, however, is whether these biomechanical characteristics actually improve clinical outcomes. In one retrospective review of patients with pelvic fractures and other risk factors for hemorrhage (unstable pattern, age > 55, or hypotension), institution of an in-hospital pelvic binder protocol did not alter the need for massive transfusion, angioembolization, or exploratory laparotomy; the 24-hour transfusion requirement; or in-hospital mortality relative to those who received no binder or, rarely, CPAS (Ghaemmaghami 2007). In a retrospective review of patients at a different institution with severe pelvic fractures, patients who received a commercial pelvic binder had significantly diminished 24- and 48-hour transfusion requirements and shorter hospital stays than those who received early anterior external fixation (Croce 2007). Additionally, there was a trend toward decreased mortality in patients who received a pelvic binder, though this was not statistically significant.

Data on the safety of circumferential pelvic compression devices, whether from CPAS or commercially available binders, is mainly limited to cadaver studies and case reports. There is a known risk of skin breakdown secondary to strain at the skin-strap interface. The force measured at the interface between the skin and the binder varies between studies and in some studies has been measured above levels thought to cause tissue damage (Knops 2010, Jowett 2007, Bottlang JOT 2002, Hendrick-

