### **Purpose of the Study**

The goal of our study is to determine whether prehospital use of a commercial pelvic binder will improve morbidity and mortality in patients with pelvic fractures. We hypothesize that prehospital placement of pelvic binders will reduce hemorrhage and need for resuscitation and will improve overall mortality in patients with pelvic fractures. Our primary outcomes will be indicators of hemorrhage (including vital signs, lactate, base excess, volume of blood products required for resuscitation, need for angioembolization or surgical control of bleeding, and length of ICU stay) and 30-day mortality. We will also measure safety events related to binder use. Additionally, we hypothesize that pelvic splinting via external compression will improve patients' pain regardless of whether they have a pelvic, acetabular, or proximal femur fracture. Pain control in the prehospital environment will be addressed as a secondary outcome in this study.

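### Readmission is counted to 30 days after injury, so days at risk depend on length of stay and survival; if either differs between arms, the comparison shifts at an equal post-discharge hazard

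*Combined protocol and SAP*

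**What the plan says.** The rule stands in the protocol under Methodology, in the paragraph on collecting data in the hospital: "Thirty days after the injury, the need for readmission and all-cause mortality within this period will be recorded". The list of Primary Outcome Variables has "Length of hospital stay" as item 10, "Need for readmission" as item 11 and "30-day mortality" as item 12. Item 11 carries no window, denominator or rule for patients who never leave hospital, so the Methodology sentence is the only definition of its time frame.

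The Data analysis paragraph describes t-tests and cross-tabulations for baseline comparability and adds "An intention to treat analysis will also be performed". It gives no method for comparing readmission, no allowance for days at risk and no treatment of death or continued stay as competing events.

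Two other places bear on whether stay or survival might differ. The Purpose of the Study states: "We hypothesize that prehospital placement of pelvic binders will reduce hemorrhage and need for resuscitation and will improve overall mortality in patients with pelvic fractures". The Background cites a retrospective review in which binder patients had "shorter hospital stays than those who received early anterior external fixation".

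**The concern.** A patient can be readmitted only after discharge. With the clock started at injury, a patient discharged on day 5 is observed for 25 days and one discharged on day 28 for 2 days. A patient who dies in hospital, or is still there on day 30, is not observed at all. Exposure for item 11 is therefore set by item 10 and, through in-hospital death, by item 12. Both are outcomes on which the trial compares the arms.

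If the binder shortened stay or kept more patients alive to discharge, its arm would accumulate more days at risk and, at the same daily risk, more readmissions. Items 10 and 11 could then point in opposite directions for an arithmetical reason, and a reader might take the excess as harm. If stay were longer in the binder arm, the shift would run the other way.

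**Working it through.** The documents state no length of stay, readmission rate or sample size, so there is no planned figure to reproduce. The only input taken from them is the 30-day window from injury. Everything else below is an assumption, chosen to show direction and rough size.

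**Set-up.** Let R be the readmission risk over 30 days after discharge, equal in both arms. With a constant hazard, h = −ln(1 − R)/30. The risk counted in the injury window for a stay of L days is 1 − exp(−h × (30 − L)).

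**Base case.** With R = 10%, h = −ln(0.90)/30 = 0.00351 per day. Take stays of exactly 10 days (arm A) and 14 days (arm B).
- Days at risk: 30 − 10 = 20 and 30 − 14 = 16.
- Arm A: 1 − exp(−0.00351 × 20) = 6.8%.
- Arm B: 1 − exp(−0.00351 × 16) = 5.5%.
- Difference 1.3 points, ratio 1.24, with no true difference.

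A hazard of 0.5% per day gives 9.5% and 7.7%, again a ratio of 1.24. Across R from 5% to 20% the ratio moves only from 1.25 to 1.23.

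**Spread of stay and shape of hazard.** Real stays vary, and readmissions may cluster soon after discharge. For the latter I used a Weibull hazard with shape 0.6, so the counted risk is 1 − exp(ln(1 − R) × ((30 − L)/30)^0.6). For variable stay I averaged the risk over an exponential distribution with the stated mean, giving zero risk to stays beyond day 30. All rows use R = 10% and mean stays of 10 and 14 days.

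| Stay | Hazard | Arm A | Arm B | Ratio |
|---|---|---|---|---|
| Fixed | Constant | 6.8% | 5.5% | 1.24 |
| Exponential | Constant | 6.9% | 6.0% | 1.16 |
| Fixed | Front-loaded | 7.9% | 7.0% | 1.14 |
| Exponential | Front-loaded | 7.7% | 6.8% | 1.13 |

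The direction is the same in every row. In the exponential rows, exp(−30/10) = 5.0% of arm A and exp(−30/14) = 11.7% of arm B are still in hospital on day 30 and could never count as readmitted.

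**Other stay differences** (fixed stays, constant hazard, R = 10%): 7 against 10 days gives 1.14, 8 against 16 gives 1.55, and 14 against 21 gives 1.76. With the front-loaded hazard these fall to 1.08, 1.30 and 1.40.

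**Survival alone.** With equal stays of 10 days but assumed in-hospital mortality of 5% and 10%, the counted risk over all randomised patients is 0.95 × 6.78% = 6.4% and 0.90 × 6.78% = 6.1%, a ratio of 1.06.

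**Window from discharge.** Among patients discharged alive, the same hazard gives 10.0% in both arms whatever the stay, a ratio of 1.00. Over all randomised patients the mortality effect remains: 0.95 × 10% = 9.5% against 0.90 × 10% = 9.0%. Moving the window removes the effect of stay but not that of survival.

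**Chance of a significant result.** At an assumed 100 patients per arm, power to detect the base-case artefact (6.8% against 5.5%) is about 6%. It would mainly distort the estimate.

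**The case against.** The strongest reply is that a fixed window from injury is a legitimate choice. It is common to both arms, keeps every randomised patient and estimates a coherent quantity: the proportion readmitted by day 30, including whatever the binder does through earlier discharge and survival. It also gives one follow-up point for two outcomes. This stands as far as it goes. But the protocol does not say that this total effect is what item 11 is meant to show, and a reader would naturally take need for readmission as a measure of what happens after discharge.

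Second, the shift needs stay or survival to differ. A reader might infer that the binder arm will show excess readmissions. The documents do not support that. They give no expected difference in stay, and the review reporting shorter stays compared binders with early external fixation, not with no binder. The other retrospective review in the Background, mainly against no binder, found no change in in-hospital mortality, transfusion or intervention. A true reduction in readmission could also offset the shift.

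Third, a reader might infer that death in hospital or a prolonged stay will be scored as a success on item 11. No coding rule says so, and such patients could be recorded as not applicable. What stands is that their handling is unspecified.

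Fourth, death and length of stay are recorded separately, so time at risk up to day 30 could largely be reconstructed at analysis. That helps only if an analysis using it is specified, and it does not capture readmissions after day 30.

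Finally, limiting the denominator to patients discharged alive conditions on an event after randomisation. If the binder saves sicker patients, its discharged group is sicker. This objection is sound and shapes the fix.

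**Conclusion.** The point holds in conditional form. The plan's only stated window for readmission makes days at risk a function of length of stay and in-hospital survival, and nothing elsewhere in the protocol corrects for this. If either differs between arms, the comparison moves against the arm with the shorter stay or better survival at an equal post-discharge hazard. Under assumed mean stays of 10 and 14 days the ratio is about 1.13 to 1.24. It would be larger for wider gaps in stay, smaller for narrower ones, and 1.00 if neither stay nor survival differs.

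The consequence is contained. Readmission is one of 16 listed primary variables and is absent from the summary of primary outcomes in the Purpose of the Study, so the main conclusions on hemorrhage and mortality do not depend on it. The 30-day window from injury is appropriate for mortality. The change is worth making because it is cheap and prevents a misleading estimate.

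**What to change.** Keep 30 days from injury for all-cause mortality. For item 11, record readmission to 30 days after discharge, and state this both in the variable list and in the Methodology sentence.

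Report the result by arm over all randomised patients as mutually exclusive categories:
- readmitted;
- discharged and not readmitted;
- died after discharge without readmission;
- died in hospital;
- not discharged by the end of follow-up, with that end defined in advance.

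This keeps the randomised comparison and shows any survival effect openly, rather than folding it into the readmission count. Give the rate among patients discharged alive only as a descriptive supplement, labelled as not a randomised comparison.

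The cost is wording in two places, an analysis table and a later record check. Follow-up closes later for long-stay patients, since the check moves to 30 days after each discharge.
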